Those who decide to participate will be asked to attend a baseline visit prior to beginning their exercise programme to determine if they are suitable. The research project will be re-explained and questions encouraged. Following this, informed consent will be obtained if appropriate. A clause outlining the conduction of an interview, voice recording and use of anonymous quotes will be included in the consent form, but this will be optional. Patients will still be able to participate in the study without completing an interview.

Baseline and follow-up visits

Baseline and follow-up visits will be completed for all research participants who complete the full intervention timeframe (i.e. 6-8 weeks). Those choosing to discontinue the intervention before completing the full intervention timeframe will be withdrawn. Follow-up visits will be completed immediately following completion of the HIIT programme, and then 12-weeks post-intervention. An additional follow-up will also be completed 4-weeks post-intervention at the Hull site only.

[figure not shown]
Travel expenses for study visits (baseline and follow-ups) will be reimbursed. Patients can be reimbursed a maximum of £75 to cover the costs of transport/parking that may be accrued.

Patients will be asked not to eat a heavy meal or smoke for 3 hours before the visit and testing (18). Patients will also be asked to dress appropriately, especially in terms of footwear and instructed to avoid unusual physical activity efforts in the preceding 12 hours (18). As testing will not be performed for diagnostic purposes, patients will not be asked to withdraw or refrain from taking any medications (18). At each study visit, the patient's medical notes will be reviewed before assessment of current and past medical history. Patients will be asked questions relating to previous medical history including previous

diagnoses, current symptoms, and medications to determine the presence of any contraindications to exercise testing (18, 19).

Resting blood pressure and HR will then be taken followed by height, weight, body mass index (BMI), waist circumference, hip circumference and waist to hip ratio. During the baseline and subsequent visits, a number of objective physiological and subjective patient-level measures will be performed.

Trial Procedures

Measurement of primary and secondary endpoints

Primary endpoint – safety, utility and tolerability

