Group 1: Patients who are eligible for the study but decide not to participate (non-consenters). The interviews will explore reasons why patients chose not to participate in the

study and whether study material could be amended to be more appealing. Patients in this group will be signposted to the relevant interview section of the patient information sheet that they have already received. Those who agree to participate in an interview will sign an interview specific consent form.

Group 2: Those who agree to participate in, and complete, the exercise programme.

The interviews will explore patient's experiences of the HIIT programme, how easy/hard they found it, whether they enjoyed it and whether they would be willing to undertake it again. They will also be asked to provide any additional information related to potential problems/barriers to the programme and any changes they may feel are required.

Group 3: Those who agree to participate but discontinue after at least one session.

Patients will be asked the same initial questions as group 1, but they will be asked why they dropped out of the programme and what could have been changed to prevent them doing so.

An interview guide with a pre-determined set of open questions will be used but the interviews will be flexible to allow the interviewer to ask further probing questions based on patient responses. All interviews will be conducted face-to-face in a private room, recorded using a Dictaphone, transcribed verbatim and anonymised. Patients will be informed that they do not have to answer any questions that they feel uncomfortable with and all responses are confidential.

Clinical outcome measures:

Pain-free and maximal walking distance:

The test that will be used starts at 2mph and 0% grade, with grade increasing by 2% every two minutes whilst speed remains constant (20). This test will be used to determine PFWD and MWD at each study visit. A stopwatch will be started when the patient walks, they will indicate to the researcher when they begin to feel IC pain, which will be recorded as PFWD. The patient will continue to walk until the pain is too severe and they need to stop, this will be recorded as MWD.

Quality of life:

Two questionnaires will be used;

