This study will utilise a cycle CPET with a ramp protocol at each study visit as a non-invasive assessment of cardiovascular function, utilising a safety protocol on the basis of the ACSM guidelines (19). Prior to the start of the test the patient will observe a 3-minute rest period whilst sitting on the cycle ergometer so that resting measurements can be obtained. After this, the patient will begin a 3-minute reference or warm-up period of unloaded cycling followed by progressive graded exercise with adequately increasing workload to induce volitional exhaustion within 8-12 minutes, concluding with a post-maximal effort recovery period (26). During the CPET, patients will be continuously monitored via a 12-lead electrocardiogram (ECG; applied after adequate skin preparation), with measurements of HR, blood pressure and rating of perceived exertion (RPE) taken at regular intervals (19). Patients will also be observed for any signs or symptoms and asked to confirm that they are asymptomatic periodically throughout (19). Upon completion of the CPET, this monitoring will continue for at least 6 minutes or until ECG changes return to baseline and significant signs and symptoms subside (19, 27). HR and blood pressure will also be monitored until they return to near resting values (19). Gas analysis will also be conducted on a breath-by-breath basis to allow determination of important secondary outcome measures such as VO_{2Peak} and VAT. VO_{2Peak} will be determined as the average oxygen uptake value during the last 30-seconds of the test whilst VAT will be estimated using the widely adopted V-slope method and verified using the ventilatory equivalents (28).

Spirometry, which will be performed prior to CPET, is an effective screening tool of general respiratory health that can be used to establish whether exercise intolerance is primarily

caused by or contributed to by ventilatory limitation (29, 30). Therefore, unforced (vital capacity; VC and inspiratory capacity; IC) and forced (forced expiratory volume in 1 second; FEV₁ and forced vital capacity, FVC) spirometry manoeuvres will be conducted, in line with American thoracic society guidelines, to substantiate the extent of any respiratory limitation during CPET (29, 30).

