The study requirements and participant expectations will be clearly explained in the patient information sheet. This will be sent to the patient and they will be given adequate time to read it at their own leisure without any pressure to partake in the study from the researcher. Informed consent will only be obtained once patients have understood all study requirements, asked any questions they may have and have agreed to participate.

Patients will be required to attend their exercise sessions 3 times per week for 6 weeks. This may be problematic for patients and may cause them to decline this intervention or withdraw once recruited. However, this may also provide a patient benefit, as this means the patient only has to attend half the number of sessions than is usually required for SEP. Furthermore, travel and parking costs may prove to be a barrier. Travel expenses for study visits (baseline and follow-ups) will be reimbursed. Patients can be reimbursed a maximum of £75 to cover the costs of transport/parking that may be accrued.

Patients will be required to attend three or four 2-3-hour study visits. This time, on top of the time required to undertake the intervention may preclude some patients from taking part in the study.

Some study elements (such as CPET or HIIT) may propose a risk to the participants. HIIT is a novel intervention in the IC population, meaning its safety is unknown. However, a large multi-centre RCT in the cardiac population (similar disease aetiology to IC) demonstrated that HIIT was a safe intervention (15). Furthermore, standards for exercise testing from the American heart association, note that the occurrence of death as a result of testing is rare with a frequency estimated at 1 per 10000 tests, maybe less (26). Therefore, although the testing and intervention procedures carry some risk, it is minimal and is outweighed by the potential patient benefits.

Sample size

Due to the pilot nature of this proof of concept study it is not possible to calculate the sample size. The main aim is to assess the conceptual benefit of the proposed interventions. We aim to recruit 20 patients from the additional Coventry site, which in addition to the target of 50 patients at the Hull site, totals 70 patients.

Descriptive statistics and statistical analysis

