Data obtained from all participants will be included in the data analysis and no data will be excluded on the basis of intervention and follow-up adherence. Therefore, all collected data at each time point will be analysed.

Baseline characteristics will be summarised descriptively using mean (\pm SD) for normally

distributed data and using median and range for non-normally distributed data. Categorical variables will be presented as frequency and percentages.

Rates of uptake, completion, dropout, adverse or serious adverse events and missing outcome data will be summarised and participation in the intervention will be described as the mean number of sessions attended and the mean time to completion (in weeks) to allow for comparison between actual and theoretical total intervention time.

In addition, tolerability will be assessed by comparing the mean heart rate achieved during each HIIT session to the 85-100% maximum heart rate range calculated from CPET.

Secondary endpoints such as changes in MWD, PFWD, VO_{2Peak} , VAT, ABPI and QoL at each time-point will be assessed using a repeated-measures general linear model.

All quantitative analyses will be conducted using the SPSS statistics software at the conventional two-sided 5% significance level with results presented as mean difference with 95% confidence intervals, associated *p* values and effect sizes where appropriate. Sub-group analysis will also be conducted comparing those who are able to give maximal effort during baseline CPET (and therefore able to perform maximal HIIT) and those who are not (therefore performing submaximal HIIT). Maximal effort will be based on previously published criteria (19, 38). Further sub-group analysis will also be performed comparing those who satisfactorily completed the intervention (i.e. completed $\geq 15/18$ sessions) and those who did not, presuming they do not withdraw from the intervention.

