The qualitative data will also be analysed using an inductive thematic analysis. Thematic analysis involves identifying, analysing and reporting themes that become apparent within the data (39). Themes collate important or patterned responses from within the data that are related to the research question (39). This means that as the researcher reads and re-reads the transcriptions, a pattern of responses will emerge that are related to the research question and can be grouped together under a theme heading. The approach will be inductive, which means that the themes are data-driven, thus emerging from the data, do not fit into a pre-existing coding frame and are not driven by the researcher's theoretical interest in the area (39).

In an attempt to minimise missing data from losses to follow-up patients will be contacted well in advance of their follow-up appointment and the researcher will attempt to rearrange any missed follow-ups. However, any missing data due to loss to follow-up will be recorded and reported adequately. Any missing data that should have been collected during a study visit will be investigated via source data and patient notes to exhaust all options. If data is still missing, it will be coded adequately during analysis and reported in results. Missing data will not be imputed by the researcher to avoid bias.

Safety reporting

Collecting and reporting data on adverse and serious adverse events will be in accordance with GCP and the Research Governance Framework v. 3.3, 2017.

Adverse events (AE)

An adverse event is any untoward occurrence that happens to a subject during the conduct of the study. The event may be as a result of the study conduct or intervention or there could be no relationship between the study and the AE at all.

Serious adverse events (SAE)

An AE is deemed serious if it:

- Results in death
- Is life-threatening (patient is at risk of death at the time of the event)
- Requires hospitalisation or prolongation of existing hospitalisation
- Results in persistent or significant disability or incapacity
- Consists of a congenital anomaly or birth defect

Hospitalisation that was planned before partaking in the study (i.e. elective surgery) should not be considered a SAE unless it has to be prolonged.

Reporting period:

The AE reporting period for each patient begins as soon as they have given informed consent for the trial and ends 30 days after their final study visit.

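### The repeated-measures model does not name its visits; with a Hull-only 4-week visit, a single model loses either every Coventry patient or all the 4-week data

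*Combined protocol and SAP*

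**What the plan says.** Under Descriptive statistics and statistical analysis, the combined protocol and SAP states that changes in MWD, PFWD, VO2Peak, VAT, ABPI and QoL "at each time-point will be assessed using a repeated-measures general linear model", in SPSS. No list of visits and no site term is given. The same section says that poor adherence to the programme or to follow-up is no reason to leave data out, and concludes that "all collected data at each time point will be analysed". On missing values it says: "Missing data will not be imputed by the researcher to avoid bias".

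The visit schedule differs by site. Baseline and follow-up visits sets a baseline, an immediate post-programme and a 12-week visit for everyone, and adds: "An additional follow-up will also be completed 4-weeks post-intervention at the Hull site only". The section on risks and barriers agrees: "Patients will be required to attend three or four 2-3-hour study visits".

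The extra visit yields endpoint data. For the treadmill test the protocol says "This test will be used to determine PFWD and MWD at each study visit", and for the cardiopulmonary test "This study will utilise a cycle CPET with a ramp protocol at each study visit".

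The targets are in the Sample size section: "We aim to recruit 20 patients from the additional Coventry site, which in addition to the target of 50 patients at the Hull site", 70 in total.

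**The concern.** SPSS's repeated-measures GLM takes one row per patient and one column per visit, and uses only patients with every column filled. The Coventry 4-week column is empty by design. The missing-data text covers loss to follow-up and measurements that were due but not obtained. It does not cover a visit that one site never schedules.

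The analyst therefore faces a choice that the plan does not settle. With four visits in the model, the secondary efficacy results of a two-centre study come from one centre. With three, the Hull 4-week measurements are collected and never analysed. In both cases, a patient who misses one modelled visit loses all their other measurements too. The choice could also be made after the data have been seen.

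**Working it through.** **Inputs.** Targets of 50 (Hull) and 20 (Coventry) come from Sample size. Four visits at Hull and three at Coventry come from Baseline and follow-up visits. The documents give no dropout rate, standard deviation or effect size, so the ranges in steps 3 and 4 are assumptions.

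**1. The plan's own total.** 50 + 20 = 70, as stated.

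**2. Perfect attendance (needs no assumption about missing visits).** Planned measurements per endpoint: 50 × 4 + 20 × 3 = 260.

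| Single model | Patients kept | Measurements used | Measurements lost |
|---|---|---|---|
| Four visits | 50 of 70 (20/70 = 28.6% lost) | 50 × 4 = 200 | 60/260 = 23.1% |
| Three shared visits | 70 of 70 | 70 × 3 = 210 | 50/260 = 19.2% |

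For the same within-patient change, and with the same SD at both sites, the four-visit model's standard error is √(70/50) = 1.18 times that from all 70 patients. The three-visit model loses no precision on the shared contrasts.

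**3. Some visits missed.** Assume that a share m of follow-up visits is missed, independently.

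- Available baseline-to-visit pairs: 70(1 − m)
- Four-visit complete rows: 50(1 − m)³
- Three-visit complete rows: 70(1 − m)²
- SE ratio: √(pairs / complete rows)

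| m | Pairs | Four-visit rows | SE ratio | Three-visit rows | SE ratio |
|---|---|---|---|---|---|
| 5% | 66.5 | 42.9 | 1.25 | 63.2 | 1.03 |
| 10% | 63.0 | 36.5 | 1.31 | 56.7 | 1.05 |
| 15% | 59.5 | 30.7 | 1.39 | 50.6 | 1.08 |

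**4. Bias when dropout depends on earlier results.** This was simulated with 600 trials in each of nine settings (dropout 5, 10 or 15%; within-patient correlation 0.5, 0.7 or 0.85). The true 12-week change was 0.50 SD. Dropout was permanent once it occurred and depended on the last observed value, with an assumed log-odds of 1 per SD.

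| Analysis | 12-week estimate (SD) | SE relative to mixed model |
|---|---|---|
| Four-visit complete rows | 0.450–0.495 | 1.16–1.27 |
| Three-visit complete rows | 0.445–0.493 | 0.97–1.03 |
| Mixed model, all observations | 0.496–0.509 | 1 |

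The mixed model here was fitted by maximum likelihood with unstructured covariance. With the weaker dependence of log-odds 0.5 per SD, large-sample complete-row estimates are about 0.46–0.50.

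**The case against.** The plan never mentions case deletion and does not say that there is only one model per endpoint. Its wording could cover separate baseline-to-visit comparisons, or a pooled three-visit model plus a Hull-only four-visit model; either would bring every scheduled visit into an analysis. The commitment to analyse everything follows a sentence about adherence, so it may not have been meant for a visit that Coventry never schedules. An analyst would probably choose the three shared visits, where the precision loss is small. The study is a single-arm proof of concept with no sample size calculation, and its primary outcomes do not use this model.

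Much of this is fair. Deletion is an inference from the named method combined with the bar on imputation. The four-visit figures are the worse case, and in the simulation the three-visit model has nearly the same precision as the mixed model. The bias result rests on an assumed dropout mechanism, and the simulated model had no site term and was not fitted by REML, so it is not exactly the model proposed below.

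The objection does not close the gap. None of the alternative analyses is specified. The adherence sentence expressly covers follow-up, and complete-row analysis removes patients for missing a follow-up visit. The two-model arrangement would still do that. The plan also promises p values, confidence intervals and effect sizes for quantitative analyses, and the study objective includes efficacy.

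**Conclusion.** The concern holds. As written, a single repeated-measures GLM cannot use both all Coventry patients and the Hull 4-week data, and neither version meets the plan's own inclusion rule. At the recruitment targets with full attendance, the loss is either 20 of 70 patients or 50 of 260 measurements per endpoint. Actual losses depend on recruitment and attendance.

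The precision cost is material only for the four-visit model: 1.18 with no missed visits, and 1.25–1.39 if 5–15% are missed independently. Bias from complete-row analysis was at most about 0.06 SD on a true change of 0.50 SD over the assumed ranges.

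Only the secondary efficacy endpoints are affected. The utility, safety and tolerability summaries are not. The point should be fixed before analysis, but it does not undermine the main purpose of the study.

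**What to change.** In Descriptive statistics and statistical analysis, replace the repeated-measures GLM with a linear mixed model (SPSS MIXED, REML) and state:

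- visit as a categorical fixed effect and site as a fixed effect;
- unstructured within-patient covariance, with compound symmetry if that does not converge;
- all available observations from both sites, with the Coventry 4-week visit declared missing by design;
- baseline-to-post and baseline-to-12-week contrasts from both sites, and the 4-week contrast labelled as informed by Hull only;
- numbers analysed by visit and site.

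In the missing-data text, add that the model imputes nothing and assumes data are missing at random. Add also that it cannot recover outcomes never measured in patients withdrawn for stopping the programme early, and report how many there are.

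A pooled three-visit model plus a pre-specified Hull-only four-visit model would settle how the 4-week visit is handled, but would still drop patients who miss one modelled visit.

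The cost is wording. Software, data collection and visits stay the same. Because the analysis section is part of the protocol, the change goes through the process described under Amendments.

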This study will use a pragmatic and flexible HIIT protocol with a higher intensity than that previously used in the IC population (12). The protocol will consist of 3 sessions per week for 6 weeks, with a work to rest ratio of 1:1 (one-minute interval of HIIT interspaced by one-minute interval of low-intensity exercise), completing 10 sets of HIIT with an overall exercise session time of 20 minutes. The intensity will be set at 85-90% PPO (from CPET) during high-intensity, (aiming to achieve 85-100% HRMax), and at 20-25%PPO during low-intensity bouts. The variation from high to low intensity will be achieved by altering the cycle cadence (rpm). This work to rest ratio has been selected as although HIIT is often prescribed in similar clinical populations using 4-minute intervals at 85-95%HRMax (33), a large RCT recently concluded that HIIT at this intensity is hardly feasible, at least not for a full 4-minutes (15). Our personal experience with cardiac patients has demonstrated that patients may exceed their peak heart rate (from CPET) during HIIT sessions. This is also likely to be the case for those with IC, especially those who are unable to achieve a maximal effort CPET. We will adopt a pragmatic approach to this by allowing it to occur but monitoring on a case-by-case basis and will reduce intensity when deemed appropriate. We will also record these occurrences to allow appropriate reporting.

The HIIT sessions will be preceded and followed by a 10-minute warm up and cool down as is standard practice in exercise rehabilitation for older adults with chronic disease. In addition, patients will be monitored for up to 10 minutes following the cool-down to ensure heart rate is returning to near resting values and/or any symptoms have subsided.

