The HIIT intervention will be performed by using a cycle ergometer with exercise prescription based on the workload achieved during a cycle CPET. The use of a treadmill may preclude patients from reaching their prescribed HIIT training zones due to the onset of claudication whilst a cycle may reduce the risk of falls in very deconditioned patients (34). It has been demonstrated that the limiting symptoms during treadmill walking were often experienced in the leg, mainly the calf, whereas the limiting symptoms during cycling were much more varied (34). Furthermore, one study, albeit small, noted that cycle testing was better tolerated than treadmill testing, which is important considering that the HIIT training zone requires the patient to exercise to near-maximal levels, similar to during a CPET (35).

Inclusion criteria:

- Community dwelling adults aged 18 or over.
- ABPI <0.9 at rest or a drop of more than 20mmHg after exercise testing
- Ability to walk unaided
- English speaking and able to comply with exercise instructions

Exclusion criteria:

- Patients who are unable to provide informed consent
- Critical limb ischaemia/rest pain
- Active cancer treatment
- Significant comorbidities precluding participation in exercise testing and/or training as per the American College of Sports Medicine Guidelines (19).
- Resting/uncontrolled tachycardia (>100bpm) and/or Resting/uncontrolled hypertension (SBP >180mmHg or DBP >100mmHg)
- Symptomatic hypotension

Additional exclusion criteria

Further to analysis of CPET results, patients will be prevented from continuing their involvement in the study if there is indication of:

- Exercise-induced ischaemia or significant haemodynamic compromise.

N.B. – Patients who are able to perform a maximal effort CPET according to previously published guidelines (19) will undergo the intervention which will be prescribed on the basis of their initial CPET. This will be referred to as maximal HIIT.

Patients unable to perform a maximal effort CPET, will still undergo the intervention which will be prescribed on the basis of their initial CPET values, but will be referred to as submaximal HIIT.

Subject recruitment

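### The maximal versus submaximal subgroup is split on effort in the baseline CPET that also supplies baseline VO2Peak, so VO2Peak change can favour the submaximal group with no change in fitness

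*Combined protocol and SAP*

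**What the plan says.** All references are to the combined protocol and SAP.

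- **Descriptive statistics and statistical analysis.** The split is prespecified: "Sub-group analysis will also be conducted comparing those who are able to give maximal effort during baseline CPET" with those who are not. Effort is judged by cited criteria, with no threshold written out, and only the baseline test is mentioned. No outcome is named for this comparison. It follows the list of secondary endpoints (changes in MWD, PFWD, VO2Peak, VAT, ABPI and QoL), none of which is excluded. Quantitative results are to carry confidence intervals and p values at the two-sided 5% level.
- **CPET/spirometry.** "This study will utilise a cycle CPET with a ramp protocol at each study visit". VO2Peak is "the average oxygen uptake value during the last 30-seconds of the test", with no requirement that effort be maximal. VAT comes from the V-slope method on the same test.
- **Additional exclusion criteria (N.B.).** "Patients unable to perform a maximal effort CPET, will still undergo the intervention", labelled submaximal HIIT.
- **High intensity interval training (HIIT) programme.** The protocol expects some patients to exceed their CPET peak heart rate in training, "especially those who are unable to achieve a maximal effort CPET".

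The plan does not grade effort at follow-up, adjust for effort, or provide a familiarisation or repeat baseline CPET. The cohort has no control group from which a retest effect could be estimated.

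**The concern.** VO2Peak, as defined here, is the uptake reached when the test ends. A test that stops short of maximal effort records a value below the patient's true peak. The subgroup is therefore defined by a feature of the baseline test that also lowers the baseline value of the outcome. The protocol accepts the same point for heart rate when it expects these patients to exceed their CPET peak in training, but the analysis section does not carry it over to VO2Peak.

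Unless effort is the same at every visit, some baseline-submaximal patients will later give fuller effort, and some baseline-maximal patients may give less. The groups then converge, which is regression to the mean caused by selecting on a component of the baseline measurement. A reader could take a larger VO2Peak gain in the submaximal group as a training response when part or all of it is a change in test effort.

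**Working it through.** The plan states no effect size, SD or power for this comparison, so there is no figure to reproduce. The check asks how large the contrast can be when fitness does not change.

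**1. Closed form**

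Inputs, all assumed because the documents give none:
- D, the under-reading in a submaximal test: 1 to 3 ml/kg/min
- p, the share of baseline-submaximal patients who stay submaximal: 0.9 down to 0.5
- q, the share submaximal at baseline: 0.4

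Formulas:
- Apparent change, submaximal group: D × (1 − p)
- Apparent change, maximal group: 0 if effort only moves upward. If upward and downward moves balance, so that q is the same at both visits, it is −D × q × (1 − p) / (1 − q)
- Spurious difference: D × (1 − p) for upward moves only, or D × (1 − p) / (1 − q) for balanced moves

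| D | p | Submaximal change | Difference, upward only | Maximal change, balanced | Difference, balanced |
|---|---|---|---|---|---|
| 1 | 0.9 | +0.10 | 0.10 | −0.07 | 0.17 |
| 2 | 0.7 | +0.60 | 0.60 | −0.40 | 1.00 |
| 3 | 0.5 | +1.50 | 1.50 | −1.00 | 2.50 |
| any | 1.0 | 0 | 0 | 0 | 0 |

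**2. Simulation of the test**

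The planned total of 70 patients (50 Hull + 20 Coventry) was used, with 4,000 runs per setting and no true change. Assumed inputs: true peak 15 (SD 4) ml/kg/min, measurement SD 1, 30% submaximal at baseline, and a mean deficit of 10% (1.5 ml/kg/min). Effort at the two visits had correlation rho, with the same distribution at each, so moves balance. The subgroup difference in change was tested at the two-sided 5% level. With two time points this is the group-by-time test of the repeated-measures model.

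| rho | Submaximal patients who become maximal | Submaximal change | Maximal change | Difference | False-positive rate |
|---|---|---|---|---|---|
| 1.0 | 0% | −0.01 | 0.00 | −0.01 | 5% |
| 0.9 | 21% | +0.14 | −0.06 | 0.19 | 9% |
| 0.7 | 37% | +0.37 | −0.16 | 0.53 | 25% |
| 0.5 | 48% | +0.57 | −0.25 | 0.82 | 44% |
| 0 | 70% | +1.05 | −0.45 | 1.50 | 84% |

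With a 20% deficit, the differences at rho 0.9, 0.7 and 0.5 are 0.38, 1.05 and 1.67, with false-positive rates of 17%, 44% and 69%.

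**3. What does and does not remove it**

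- Adjusting for baseline VO2Peak: at rho 0.5 and a 10% deficit, 0.70 of the 0.82 remains.
- Testing the subgroup-by-visit interaction: this is the test simulated above, so it carries the full bias.
- Limiting to patients maximal at both visits: mean change is about 0.00 (−0.01 to +0.01) in every setting. By definition this set contains no baseline-submaximal patient, so it validates VO2Peak change in the maximal group and says nothing about the contrast.

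**The case against.** The strongest objection is that the target is inferred. The plan names no outcome for this comparison and does not say that it is meant to show whether submaximal HIIT works as well as maximal HIIT. Of the six outcomes listed, MWD and PFWD come from a treadmill test, and ABPI and QoL do not come from the CPET. VAT does, but it is not read off the end of the test as VO2Peak is. This stands: only VO2Peak clearly carries the artefact. VO2Peak is nonetheless a listed secondary endpoint that nothing excludes, so its use is the natural reading.

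Second, inability to reach maximal effort may be a lasting symptom limit, in which case the bias is zero. That also stands as a possibility, but the plan does not check it although CPET is repeated at every visit.

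Third, a reader might infer that any convergence happens regardless of HIIT. The documents do not support that. Better tolerance of exercise after six weeks of training could itself be a treatment effect, so not every move to fuller effort is spurious. The plan as written cannot tell the two apart.

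Fourth, the balanced-moves figures need the submaximal share to stay constant. If familiarity mainly raises effort, the upward-only column is the relevant one: 0.6 rather than 1.0 in the middle case.

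**Conclusion.** The concern holds for VO2Peak in the maximal versus submaximal comparison. One baseline test sets the group and supplies the starting value, and nothing in the plan tracks effort afterwards. The direction is clear if effort changes in the ways modelled: it favours the submaximal group. The size is not known. Under the assumed inputs it is about 0.1 to 1.5 ml/kg/min with upward moves only, 0.17 to 2.5 with balanced moves and 40% submaximal at both visits, and 0 with fully stable effort. The false-positive rates depend on similar assumptions.

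A reader might go further and conclude that the whole subgroup finding could be reversed, or that the trial's main result is at risk. The documents support neither. The primary endpoints are utility, safety and tolerability, and none uses this contrast. The other subgroup outcomes are not shown to carry the artefact. This is one secondary outcome in a subgroup analysis that is exploratory in character, within a proof-of-concept cohort. It merits correction before analysis because the plan would otherwise report the contrast with a p value and no warning.

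**What to change.** Amend the analysis section as follows.

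1. State the maximal-effort criteria and apply the same ones to every CPET, at baseline and at each follow-up.
2. Cross-tabulate baseline by follow-up effort for each follow-up visit, and show VO2Peak change within those cells.
3. Name the outcomes for the subgroup comparison. Base its conclusion on those less tied to CPET effort: VAT where it can be determined, and treadmill MWD and PFWD.
4. If the VO2Peak contrast is still reported, label it as confounded by test effort.
5. Report VO2Peak change among patients maximal at both visits, if wanted, as a check on the maximal group only.

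The cost is small. Gas analysis, heart rate and perceived exertion are already planned at every CPET, so no test, visit or patient is added. There is one extra table and a few lines of text. The cells may be small with 70 patients, so they should be read descriptively. VAT may be missing in some tests stopped early; the documents do not show how often it can be determined, and its availability should be reported by effort group.
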